## **An Open-Label Trial of Triheptanoin in Patients with Glucose Transporter Type-1 Deficiency Syndrome (GLUT1 DS)**

### **1.0 GOALS AND OBJECTIVES**

- 1.1 The primary objective of the study is:
- To evaluate the safety of triheptanoin via adverse event rates and laboratory values.
- 1.2 The secondary objective of the study is:
- To evaluate the long-term efficacy of triheptanoin as measured by the change in seizure frequency from historical baseline.

### **2.0 BACKGROUND AND SIGNIFICANCE**

#### **2.1 Disease Background**

Glucose Transporter Type-1 Deficiency Syndrome (GLUT1 DS) is a devastating disease characterized by seizures, developmental delay and movement disorder. It is caused by a mutation in solute carrier family 2, member 1 gene (SLC2A1), which encodes for glucose transporter type-1. This protein transports glucose from blood into the brain. Because glucose is the primary source of energy for the brain, this disorder results in a chronic state of energy deficiency in the brain. Current treatment consists of ketogenic diet, which generates ketone bodies that provide an alternative energy source to glucose. However, ketogenic diet is difficult to tolerate and some patients are not compliant with or are otherwise not on the diet. As such, in order to improve control of break-through seizures, patients may require one to two antiepileptic drugs (AEDs).

#### **2.2 Supporting Previous Studies**

##### *2.2.1 Nonclinical Studies*

Triheptanoin, which is the name of the substance to be provided by the Company and is under investigation in this trial, is synonymous with other names for the same substance which have been the subject of investigations published in the scientific and medical literature. A number of in vitro and rat studies have been conducted with triheptanoin by research investigators. Triheptanoin is likely hydrolyzed in the intestine and the heptanoate and glycerol absorbed efficiently in the rat liver. The 7 carbon heptanoate is cleaved to two acetyl-CoA and one propionyl-CoA. These are metabolized to several possible compounds including C4 and C5 ketone bodies, which can distribute via the circulation and can be taken up by the brain and muscle. Some propionyl-CoA will be converted to succinyl-CoA to refill the TCA cycle, and some will be converted, via the TCA cycle, to oxaloacetate to generate glucose via gluconeogenesis.

In a study of the biochemical effects of triheptanoin in the brains of a mouse model of GLUT1 DS, gluconeogenesis in the brain was established based on the presence of radiolabeled glucose after intravenous infusion of radiolabeled heptanoate. In addition, intravenous infusion of radiolabeled heptanoate led to higher levels of acetyl-CoA and glutamine in the brain of G1D mice relative to normal mice. Brain glutamine concentration and C enrichment were also greater when compared with glutamate in both animal groups, suggesting that heptanoate and/or C5 ketones were primarily metabolized by glia. The effects of triheptanoin on the seizure activity in this mouse model have not yet been reported.

Triheptanoin has been found to be effective in 4 of 7 animal models of epilepsy. In the corneal kindling chronic model, triheptanoin delayed development of kindled seizures in a dose-dependent manner, but did not protect against fully kindled seizures. In the chronic model of PTZ (pentylenetetrazole) in pilocarpine-status epilepticus, triheptanoin partially reversed the lowered PTZ threshold for tonic seizures but not clonic seizures in the chronic stage. In the maximal electroshock threshold model, triheptanoin increased the seizure threshold. In the genetic mouse model of generalized epilepsy due to the GABA-A-gamma2(R43Q) mutation, triheptanoin halved the time spent in seizures and reduced the frequency of seizures caused by insulin-induced hypoglycemia. However, triheptanoin was not effective in the fluorothyl, pentylenetetrazole nor 6Hz models. The efficacy of triheptanoin in some but not all animal models of epilepsy is similar to that found with other AEDs.

In toxicology studies, there were no toxic effects on animal growth, lipid digestibility, clinical chemistry parameters, or the histopathology of liver, kidney and small intestine in rats fed for 9 months with triheptanoin at levels that replaced up to 50% of the standard soybean oil in rodent chow. Hepatic steatosis and alterations in intestinal villi were the only findings observed in a single 9 month repeat dose oral rat toxicology study. The findings may be due to the effect of extreme fat overload compared with the normally low fat intake in rats (~10-fold normal fat intake) and the efficient direct absorption, non-bile-dependent of triheptanoin and metabolites. This adverse effect has not been observed in previous human clinical trials in which FAOD patients have shown the opposite finding, a reduction in hepatomegaly/steatosis, with triheptanoin treatment.

Triheptanoin has been generally well tolerated when administered to subjects with all subtypes of FAOD. Some subjects have had difficulties with gastrointestinal upset or have diarrhea when taking the oil. Small doses and mixing with foods or drinks is important in tolerability. Many of the serious adverse events (SAEs) reported for these subjects involved events consistent with FAOD (e.g., muscle weakness or pain, myoglobinuria, rhabdomyolysis, metabolic crisis or decompensation, cardiomyopathy, hypoglycemia, elevated CK), often in association with events known to precipitate metabolic crises in these patients, such as infections (e.g., upper respiratory infection, flu, cold, urinary tract infection, gastrointestinal illness) or exercise, or during periods of limited triheptanoin treatment. Other SAEs involved events such as infections without reported FAOD exacerbation, fever and/or vomiting from unspecified cause, respiratory distress/breathing problems, falling oxygen saturation rate, seizure, or medical procedures apparently unrelated to FAOD. Almost all of the reported SAEs were considered unrelated to triheptanoin treatment. Triheptanoin has been administered in 44 pediatric subjects with LC-FAOD. Of these, three subjects had treatment initiated between the ages of 0-1 month, eight between ages 1 month-2 years, 29 between ages 2-12 years, and four between ages 12-16 years. Twenty of these subjects had triheptanoin treatment for over five years. The safety profile in pediatric subjects is similar to that found in adults, with ADR consisting of GI disturbance and excess

weight gain (Section 5.4 of Investigator Brochure).

Triheptanoin is being studied in approximately 30 GLUT1 DS subjects in a clinical trial sponsored by [name] at the University of Texas, Southwestern. The study is ongoing and no results have been published, although public reports from patient families have suggested significant benefit in seizure reduction and development improvement.

### **2.3 Protocol Rationale**

GLUT1 DS results in insufficient transport of glucose into the brain. The rationale for triheptanoin treatment in GLUT1 DS is that:

- 1) Triheptanoin is metabolized to heptanoate and C4 and C5 ketone bodies. These metabolites provide an alternative energy source to the brain
- 2) Triheptanoin has the ability to provide succinyl-CoA via propionyl-CoA in order to resupply intermediates of the citric acid cycle (i.e., anaplerosis). In contrast, ketogenic diet and medium chain triglyceride (MCT) oil provide only even-carbon chain ketone bodies and fatty acids, neither of which can be anaplerotic
- 3) Triheptanoin treatment has the additional potential advantage over ketogenic diet in that ketogenic diet requires severe restriction of carbohydrate intake, which leads to reduced serum glucose; this state of low normal serum glucose further exacerbates the glucose deficiency in the brain and partially offsets the benefits of ketone body generation. In contrast, triheptanoin treatment allows for greater carbohydrate intake and higher serum glucose levels relative to ketogenic diet and thus does not exacerbate the deficiency of glucose transport into the brain.

Because of the difficulties in maintaining a ketogenic diet, some patients are not able to comply with or tolerate the diet. These patients represent the subgroup of GLUT1 DS patients who are most in need of an alternative therapy to ketogenic diet.

### **3.0 STUDY DESIGN**

This is an open-label study to assess the safety and efficacy of triheptanoin in patients with GLUT1 DS over a four (4)-year initial treatment period with a one (1)-year extension period.

#### **3.1 Study Population**

The study will enroll GLUT1 DS patients (between 1 and 50 years of age) who are currently not on ketogenic diet or medium chain triglycerides (MCT). Eligible patients may be those who (1) have participated in a prior clinical trial of triheptanoin, or (2) are naïve to

triheptanoin and not eligible for another trial.

### 3.2 Number of Subjects Planned

The study will enroll up to 50 subjects in total.

### 3.3 Study Timeline

The total duration for individual subjects is five (5) years, including four(4) years with eight (8) visits to the clinical site during the initial treatment period and one (1) additional year in the extension period. After a two-week Screening period, subjects will enter the initial treatment period on one of two schedules. Study Visit window will be +/- 2 weeks from the scheduled date.

#### 3.3.1 Schedule A:

For subjects previously treated with triheptanoin the visit schedule will be as follows, with telephone follow-up between visits as needed: (Table 1)

#### 3.3.2 Schedule B:

For subjects who are naïve to triheptanoin, the visit schedule will be as follows with telephone follow-up between visits as needed:(Table 2)

## **4.0 SELECTION AND ENROLLMENT OF SUBJECTS**

### **4.1 Inclusion Criteria**

Individuals eligible to participate in this study must meet all of the following criteria:

- 1) Patients with GLUT1 DS by physician diagnosis
- 2) Males and females, aged 1 to 50 years
- 3) Allowed to be on concomitant AEDs
- 4) Patients are able to tolerate triheptanoin if they have been (or are currently being) treated with this medication
- 5) Must, in the opinion of the investigator, be willing and able to comply with study procedures and schedule
- 6) Provide written assent (if appropriate) and written informed consent by a Legally Authorized Representative (LAR) after the nature of the study has been explained, and prior to any research-related procedures
- 7) Sexually active subjects must be willing to use an acceptable method of contraception while participating in the study
- 8) Females of childbearing potential must have a negative pregnancy test at Screening and be willing to have additional pregnancy tests during the study

### **4.2 Exclusion Criteria**

Individuals who meet any of the following exclusion criteria will not be eligible to participate in the study:

- 1) Patients and their Legally Authorized Representatives (as appropriate) not willing or able to give written or verbal assent or written informed consent.
- 2) Concomitant administration of a ketogenic diet for the treatment of GLUT1 deficiency at time of study drug initiation
- 3) Concomitant administration of valproic acid
- 4) In the Investigator's opinion, the patient may not be compliant
- 5) Pregnant or breastfeeding an infant at screening
- 6) Has a concurrent disease or condition, or laboratory abnormality that, in the view of the Investigator, places the subject at high risk for adverse events, or introduces additional safety concerns
- 7) History of or current suicidal ideation, behavior and attempts
- 8) Patient qualifies for any other clinical trial designed to progressively evaluate the safety and efficacy of triheptanoin as approved by the FDA under a separate IND which is open at Cook Children's

### 4.3 Consent Procedures

Informed consent and assent will be obtained following an informed consent conference wherein the principal investigator or their IRB-approved designee will discuss with the LAR the purpose of the study, procedures to be followed, the duration of participation, alternate modes of treatment, and the risks and benefits of participation, as described in the consent form.

A signed consent form will be obtained from the LAR for each enrolled subject. As per the Cook Children's IRB guidelines, written assent from a minor aged 13-18 and verbal assent from a minor aged 8-12 will be obtained. The patient and LAR will be provided written copies of both the informed consent and assent documents. The signed original consent and assent documents will become a part of the permanent medical record and copies will be provided to the patient and LAR. A consent note will be completed and placed in the subject's research chart to document properly-obtained consent.

This study will be conducted in compliance with all United States Federal and local laws, regulations, and guidelines for the conduct of research in a vulnerable population.

## 5.0 METHODS

[figure not shown]
### 5.1 Recruitment of Subjects

Eligible patients will be identified either from the outpatient neurology clinic or inpatient neurology population at Cook Children's Medical Center; or patients who are referred for treatment for their GLUT 1 DS. Recruitment of subjects will be performed by the principal investigator or their IRB-approved designee.

### 5.2 Sources of Research Material

#### 5.2.1 Investigational Product

An investigational form of triheptanoin will be utilized as study drug. This form of triheptanoin is a highly purified form intended for oral administration. It is a medium chain triglyceride of three seven-carbon fatty acids whose formula is:

|   |  |
|---|--|
| Protocol Number: 2013-NEUR-001
Version: 4.1
23-Mar-2018 |  |
|---|--|

This investigational form of triheptanoin is being developed by Ultragenyx Pharmaceutical Inc. as a substrate replacement therapy for the treatment of long-chain fatty acid oxidation disorders (LC-FAOD) and GLUT1 DS.

### 5.2.2 Mechanism of Action

Triheptanoin is metabolized to heptanoate and C4 and C5 ketone bodies. These metabolites bypass the GLUT1 transporter to cross the blood-brain-barrier and provide an alternative energy source to the brain. These metabolites also have the ability to provide succinyl-CoA via propionyl-CoA in order to resupply intermediates of the citric acid cycle (i.e., anaplerosis) within the brain.

### 5.2.3 Dose and Mode of Administration

Triheptanoin is colorless to light yellow oil. Triheptanoin will be administered orally (PO) with food or by gastrostomy tube at least four times per day (breakfast, lunch, dinner, and before bed), comprising 35-40% of total calories titrated to a maximum tolerated dose level. The dose may be divided into smaller more frequent doses with food as needed. The dose may be mixed with small amounts of food or drink as indicated in the administration guideline provided by Ultragenyx.

The rationale for the chosen dose (1-4 g/kg of body weight per day divided into 4 doses) is based on the demonstrated safe and effective use of triheptanoin at the suggested dose in patients with Fatty Acid Oxidation Disorders.

## 5.3 Duration of Treatment

Duration of the initial treatment is 4 years with an additional one-year extension period.

Triheptanoin will be provided to the patient by the CCMC Investigational Drug Service pharmacy (IDS pharmacy) during visit 1 and at all scheduled clinic visits. In lieu of dispensation at time of study visit, the IDS pharmacy may choose to ship either a 3-month or 6-month supply to patients, as prescribed by the PI.

## 5.4 Study Procedures

The dose will be ~35-40% of total caloric intake (~1-4 g/kg/day, depending on age), for up to 5 years, including the extension period, with a visit to the clinical site at day 1, Months 3, 6, 12, 18, 24, and annual thereafter for both groups. Enrolled subjects are otherwise able to maintain standard of care treatment which may include anti-epileptic drugs (AEDs) throughout the duration of the study.

Up to 50 patients with a diagnosis of GLUT1DS who have or have not been previously on Triheptanoin will be enrolled based on their prior treatment status.

During a two-week screening period, subjects will record daily seizures and diet (last three days) in a diary to serve as a baseline measurement. If a patient has recorded all screening criteria prior to consent, that data may be used in lieu of additional screening. If, in the opinion of the Investigator, a patient who is currently on the ketogenic diet would be placed at potential risk for compromise of patient safety by stopping ketogenic diet for two weeks before initiation of treatment protocol, the two-week screening period from consent to initiation may be waived by the Investigator. In the instance of waiving the screening period, seizure and diet information will be gathered retrospectively via parent/patient interview. After the Screening period, subjects will enter the treatment period on one of two protocol schedules. Study Visit window will be +/- 2 weeks from the scheduled date.

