##### 5.4.4.2 Laboratory

Blood samples will be collected for CBC, Chem-7, ALT/AST, at Screening, Week 13, and every six months through the end of year 2, and annually thereafter for all subjects.

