#### 11.2 *Efficacy Analysis*

For efficacy analysis, seizure frequency expressed as the number per month will be calculated during treatment and compared to the historical seizure rate prior to treatment with triheptanoin. Change from baseline will be expressed as median percent reduction in baseline seizure frequency.

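### Patients who come off ketogenic diet to enter the study have no defined seizure baseline, so their seizure and glucose changes can include the effect of stopping the diet, in either direction

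*Combined protocol and SAP*

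**What the plan says.** **Who can enter.** Section 3.1 describes the population as patients who are off ketogenic diet. Section 4.2 excludes the diet only at the point where study drug starts. Section 5.4 writes a procedure for a patient who is on the diet. Screening, which lasts two weeks, may be waived if the investigator thinks the patient "would be placed at potential risk for compromise of patient safety by stopping ketogenic diet for two weeks before initiation of treatment protocol".

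**Where the seizure baseline comes from.** Section 5.4 has the diary kept over the two screening weeks as a baseline. If screening is waived, "seizure and diet information will be gathered retrospectively via parent/patient interview". Data already recorded before consent may replace screening altogether.

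**What the diet is.** Section 2.1: "Current treatment consists of ketogenic diet, which generates ketone bodies that provide an alternative energy source to glucose".

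**How efficacy is summarised.** Section 11.2 says that on-treatment seizure frequency is "compared to the historical seizure rate prior to treatment with triheptanoin", then reports one median percent reduction from baseline frequency. Section 1.2 also names a historical baseline. Neither section gives its source, its window or the diet status during it, and no split by prior diet is planned. No control arm is described (Section 3.0), and up to 50 subjects are planned (Section 3.2).

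**Laboratory baseline.** Section 5.4.4.2 has blood drawn "at Screening, Week 13, and every six months through the end of year 2" and yearly after that. Tables 1 and 2 put Screening at day -14 and show no draw at Visit 1. Glucose is in the chemistry panel in the table footnotes. Section 11.1 tabulates change from Baseline. Section 2.3 says that "ketogenic diet requires severe restriction of carbohydrate intake, which leads to reduced serum glucose".

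**The concern.** Call a patient who is on ketogenic diet at consent and stops it for the study a switcher. Three kinds of pre-treatment rate are then possible: a diary kept after an active treatment has been removed, a recalled rate that probably covers time on that treatment, or records from before consent with diet status unspecified. For switchers, the choice between the first two turns on the investigator's judgement of risk. These rates do not measure the same thing, yet Section 11.2 would combine them.

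With no control arm, the pre-treatment rate is the only comparator for efficacy. Section 7.1 also keeps seizures related to GLUT1 deficiency out of adverse event recording. A switcher who ends worse than on the diet would therefore have to be seen in the seizure comparison, where the choice of baseline could hide it.

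The glucose question is the same on a smaller scale. Screening is the only scheduled draw before dosing. A switcher's Screening value may still reflect the diet, so the change from Baseline would include the change of diet. Section 1.1 makes laboratory values part of the primary safety objective.

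**Working it through.** The documents state no seizure rate, effect size, power or number of switchers, so there is no planned figure to reproduce. Apart from the planned 50 subjects, every number below is an assumption chosen to show direction and scale.

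**1. One switcher.** Set the on-diet rate to 1, the rate in the diet-off run-in to w, and the rate on triheptanoin to t.

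- Reduction against the run-in diary = 1 - t/w
- Reduction against on-diet recall = 1 - t

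| w | t = 1: against run-in | t = 1: against on-diet recall | t = w: against run-in | t = w: against on-diet recall |
|---|---|---|---|---|
| 1.25 | 20% | 0% | 0% | -25% |
| 1.5 | 33% | 0% | 0% | -50% |
| 2 | 50% | 0% | 0% | -100% |
| 3 | 67% | 0% | 0% | -200% |

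The same patient gives a different answer by route. For example, with 4 seizures a month on the diet and 5 on triheptanoin, a run-in rate of 6, 8 or 10 gives 1 - 5/6 = 17%, 1 - 5/8 = 38% or 1 - 5/10 = 50% reduction. Against the on-diet rate the result is 1 - 5/4 = -25%, a worsening.

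**2. Direction.** Whether the run-in figure is wrong depends on what w represents.

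- If w is a stable diet-off rate, 1 - t/w is a fair estimate of triheptanoin against no diet.
- If w is a transient rebound, 1 - t/w is too large.
- If the diet's effect lingers through the two weeks, the diary rate is too low. Take a stable diet-off rate of 2 and t = 1: the reduction against no diet is 1 - 1/2 = 50%, but a diary rate still at 1 gives 1 - 1/1 = 0%.
- On-diet recall shrinks or reverses the figure relative to no diet.

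**3. Effect on the pooled median.** A simulation used 50 subjects and 3,000 runs. Underlying 14-day rates were log-normal with median 20 and log-scale standard deviation 0.8, and counts were Poisson. No subject had a drug effect. All switchers had a run-in diary at w times their usual rate and then returned to that rate.

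| Share of switchers | w = 1.5 | w = 2 |
|---|---|---|
| 0% | 0.0% | -0.1% |
| 10% (5 of 50) | 3.0% | 3.8% |
| 20% (10 of 50) | 6.6% | 8.4% |
| 40% (20 of 50) | 14.9% | 22.1% |
| 100% | 33.4% | 50.2% |

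This is the case that inflates the result most simply: every switcher takes the diary route and the rebound is wholly transient. In the same case, on-diet recall would give 0% for a switcher (t = 1), so a mixture of routes would move the median less.

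**4. Glucose.** No figure can be computed. Sections 2.3, 5.4.4.2 and 11.1 together show that the diet lowers glucose, that the only scheduled pre-dose value is two weeks before dosing, and that change is measured from there. The documents do not say by how much glucose would move.

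**The case against.** The strongest reply is that Sections 1.2 and 11.2 name a historical rate, not the screening diary. For subjects already taking triheptanoin (Schedule A), the diary is on-drug and cannot be their rate before treatment. A historical rate from before the diet would not carry this problem. This stands against any claim that the run-in is the efficacy baseline. It does not remove the point: Section 5.4 calls the diary a baseline, Section 11.2 moves from the historical rate to baseline frequency without defining either, and nothing requires a pre-diet rate.

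Next, the two-week diet stop is inferred from a waiver clause, no section instructs it, and Section 3.1 suggests that switchers may be few. Both are fair and limit the size of the point.

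Third, the objective is change from a historical baseline, not benefit over the diet, so a stable diet-off rate is a legitimate reference. That also stands, and it is why the on-diet rate should not be the only comparator for switchers. But the plan requires no stable diet-off period before the diary.

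Fourth, prior and concomitant therapies are already collected at Screening and at every visit. Diet history may therefore be in the data, but no analysis uses it.

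On glucose, a reader might infer that every later value is off the diet. Section 4.2 bars the diet only when drug starts, so the documents do not establish that. Section 2.3 also speaks of low normal glucose, so counts of abnormal results need not move; the descriptive change is what is affected. The documents tie the diet to glucose and give no basis for extending the point to other analytes.

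**Conclusion.** The plan does not fix the pre-treatment seizure rate for switchers, and its three possible sources are not comparable. The reported reduction can include the effect of stopping the diet. A transient rebound in the run-in would inflate it; an on-diet rate or a lingering diet effect would shrink or reverse it. The descriptive glucose change in switchers can include the diet change too.

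A reader might infer that the seizure reduction is biased in triheptanoin's favour. The documents do not support that: the comparator is undefined, the routes push in opposite directions, and no evidence of rebound is given. The net effect is unknown. Under the assumptions above it is about 3 to 4 percentage points of pooled median with 10% switchers and 15 to 22 with 40%, and it is nil if there are none. The change should be made because it costs little and the pooled figure cannot be interpreted for switchers without it.

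**What to change.** - **Sections 3.1, 4.2 and 5.4:** reconcile the statements on whether, and until when, a patient may be on ketogenic diet. This is for the sponsor to settle.
- **Section 5.4:** for every subject, record diet status at consent, diet stop date and baseline source. For subjects on the diet at consent, obtain the seizure rate before stopping, through the interview already provided for, whether or not screening is waived.
- **Section 11.2:** define the pre-triheptanoin baseline by source, window and diet status, and state what it is for subjects already on triheptanoin, whose screening diary is on-drug. Base the main median percent reduction on subjects not on ketogenic diet at consent. Use the stop dates to identify, and show separately, those who stopped shortly before the diary, with that interval set in advance. Report switchers in their own row against both their on-diet rate and, where available, their diet-off diary rate.
- **Section 11.1:** tabulate change from Baseline in glucose separately for switchers.

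The cost is a few data fields, one interview item and some extra table rows. The main efficacy group becomes somewhat smaller, and the switchers' on-diet rate is recalled, not recorded prospectively.
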